11.3 CONCEALMENT MECHANISM AND IMPLEMENTATION

On the prenatal visit an investigator randomizes included patients (after they signed the IC) and gives them a study number as described in section '13.4 confidentiality and access to data'. A pop up in their electronic file and all the 4 questionnaires are kept together in one plastic sheet (one folder with 4 questionnaires per patient: registration checklist, informed consent, data collection form and refusal questionnaire) in a closet of the prenatal visit. Every day all folders of included patients are moved from the prenatal visit to the maternity ward (by the study nurse) where there is also a predetermined closed closet to store all the forms.

When the patient arrives on the labor ward to give birth (due day) the midwives are aware of their participation in the study thanks to the pop up in their electronic file. On this day, we explain again the study to the patient and give them the possibility to drop out. The reason why is always noted on Questionnaire 4 (refusal questionnaire).

The investigators (AB, LP, IS , FP) will not be blinded to the allocation because they can see if patients have the VRH experience or not during measurements.

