10. SELECTION AND WITHDRAWAL OF SUBJECTS

During the prenatal visit (PNV = T0; some weeks before the due date) the pregnant women receive information about the the study and the use of VRH from the midwife. Each patient will be asked for participation in the study, after verifying the presence of the inclusion criteria and absence of any exclusion criteria. The registration checklist is filled in (questionnaire 1). If patients refuse, their motivation will be noted on the refusal questionnaire(questionnaire 4). All the included patients receive sufficient information and time to decide if they want to participate or not. After signing the informed consent (Questionnaire 2 resp) they will be immediately randomized using block randomization (with excel). This will assign the pregnant woman to either control group or the VRH group.

On the day of delivery every included patient will receive standard of care. When the women selected in the VR group are in active labor (NRS pain ≥ 4 , cervical dilatation ≥ 4 cm and regular contractions (every five minutes) we present the VRH treatment (T1).

Patients who refuse the VRH treatment (T1) or remove the VRH headset during(T2) will be asked to fill in questionnaire 4 (refusal questionnaire). They will be considered as drop outs.

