11.2 SEQUENCE GENERATION

We created a block randomization in excel. This block randomization, has variable block sizes to decrease the chance of deducing the following allocation. The patients will be randomly allocated in either the either the control group or the VRH group in a 1:1 allocation.

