13.3 CONSENT OR ASSENT

Every investigator will be taking part in the recruitment of the patients.

Each includable patient will be approached on the prenatal visit and asked for participation in the study, after verifying the inclusion criteria and the absence of the exclusion criteria.

The investigators will present the study to the patients, using a patient oriented explicatory form, after which they will look at the informed consent together with the patient.

They will receive the following information:

- The aim of this research
- The duration of their participation in this research
- Their participation has to be based solely on their own free choice
- Profits that may result from the research
- Demonstrates how medical care will be continued at the end of the research, in case of premature termination of the research and in case of exclusion from the research, where applicable
- Confidentiality of data and the possibility to withdraw from the research at any time.

If necessary they will give the patient some time to reflect and come back to sign and collect, or not, the informed consent. After signing by the patient and the investigating physician, a copy of this document will be given to the individual research participant. The investigator must keep a second copy of the signed informed consent in the archives for a minimum of 15 years.

See appendix 17.1 'Informed consent'.

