13.4 CONFIDENTIALITY AND ACCESS TO DATA

Every patient gets a code to anonymize her. The code will be a tree number code following VRH4L (VRH4L XXX) Information leading to their identity will be kept in the protected database file.

This database is only accessible to the lead investigators. (requiring a password)

The IC forms and data forms will be kept in a closet with very limited access.

See appendix 'Clinical study agreement' Article 9 'Data privacy' and Article 5 'Confidentiality'.

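### Section 11.3 is headed as a concealment mechanism but gives none, so nothing in the plan stops a recruiting investigator from seeing the next allocation

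*Combined protocol and SAP*

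**What the plan says.** Four sections describe the path from list to allocation.

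- **Section 11.2, on generation:** "We created a block randomization in excel". No role is named for the person who made the list. The stated safeguard is: "This block randomization, has variable block sizes to decrease the chance of deducing the following allocation". The block sizes are not given.
- **Section 10, on timing and tool:** "After signing the informed consent (Questionnaire 2 resp) they will be immediately randomized using block randomization (with excel").
- **Section 11.3, on who assigns:** "On the prenatal visit an investigator randomizes included patients (after they signed the IC"). The rest of the section covers study numbers, storage of the patient folders, the alert in the electronic file, the repeat explanation on the labor ward, and why investigators are not blinded.
- **Section 13.3, on recruitment:** "Every investigator will be taking part in the recruitment of the patients", and "The investigators will present the study to the patients, using a patient oriented explicatory form". Section 10 adds that "the pregnant women receive information about the the study and the use of VRH from the midwife".

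The only access restriction on a file is in section 13.4 (confidentiality): "This database is only accessible to the lead investigators. (requiring a password"). It concerns the database that links codes to identities, not the randomization list.

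**The concern.** Concealment and blinding are different protections. Blinding concerns who knows the assignment once it is made. Concealment concerns whether the person deciding to approach, screen or enrol a woman can know what she would receive. Section 11.3 accepts that blinding is impossible, which is reasonable for a headset. That makes concealment the main remaining defence of the comparison, and the section does not describe it.

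If a recruiter knows the next allocation, enrolment can be steered, knowingly or not, toward women expected to do well with VRH or away from those who are not. The plan leaves some room for this. Complicated pregnancy is an open-ended exclusion, dizziness is a matter of judgment, and section 13.3 lets a woman take time and return to sign, so the order of enrolment can shift. The primary outcome is a self-reported change in NRS pain (section 5.1) in a trial of 38. Analysis cannot reliably repair selection at entry.

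**Working it through.** **1. The procedure, step by step.**

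| Step | What the plan states | What it leaves open |
|---|---|---|
| Generate the list | Made in Excel by the protocol team (11.2) | Which person, and whether that person recruits |
| Hold the list | Nothing | Who keeps the file and who can open it |
| Approach and consent | All investigators take part (13.3); the midwife gives first information (10) | Whether any of them can see the list |
| Assign | An investigator, straight after consent, with Excel (10, 11.3) | Whether later rows are visible when one is used |

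The closets in section 11.3 hold patient folders. The password in section 13.4 protects another file, and the lead investigators who have it are also recruiters under section 13.3.

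**2. What the existing safeguards do.**

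- Variable blocks hinder deduction from past assignments. They do not affect someone who can read ahead.
- Assignment after consent fixes the order of those two steps. The decisions to approach, screen or defer come before both.
- Sections 10 and 13.3 say that eligible women are all to be asked, and refusals are logged. This limits selective approach, but no record is described for women who were never approached.

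**3. Guessing when the list is unseen.** Block sizes are not stated, so they are assumed. The simulated recruiter knows past assignments, always guesses the arm that is behind, and tosses a coin when the arms are level.

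| Assumed block sizes | Correct guesses | Of 38 |
|---|---|---|
| 2, 4 | 72% | 0.72 × 38 ≈ 27 |
| 2, 4, 6 | 70% | 0.70 × 38 ≈ 27 |
| 4, 6 | 69% | 0.69 × 38 ≈ 26 |

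Chance gives 19 of 38. A readable list would give 38 of 38. The fair contrast is therefore about 70% against 100%.

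**4. The plan's own sample size.** Section 11.1 uses a difference of 2, SD 2, two-sided 5% and power 80%. With noncentrality = (difference / SD) / √(2/n) and 2n − 2 degrees of freedom:

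- n = 16: 1 / √(2/16) = 2.83, power 0.781
- n = 17: 1 / √(2/17) = 2.92, power 0.807

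So 17 per arm reproduces. Then 17 / 0.90 = 18.9, rounded up to 19 per arm and 38 in total. This figure is not disputed.

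**5. False-positive rate under an assumed imbalance.** Set the true effect to zero and let selection shift the expected outcome between arms. Same formula, n = 17, 32 degrees of freedom, critical value 2.04:

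| Assumed shift (points) | In SD units | Noncentrality | Two-sided rejection rate |
|---|---|---|---|
| 0 | 0 | 0 | 5.0% |
| 0.2 | 0.10 | 0.10 / 0.343 = 0.29 | 5.9% |
| 0.5 | 0.25 | 0.25 / 0.343 = 0.73 | 10.9% |
| 1.0 | 0.50 | 0.50 / 0.343 = 1.46 | 29.3% |

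The shifts are assumptions. The SD is the section 11.1 value for the NRS, applied here to the outcome as the plan applies it.

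**The case against.** The strongest reply is that this is silence, not a described flaw. A reader might infer that the recruiting investigators made the list, hold it, and can read every upcoming row. The documents do not support that. Section 11.2 says only that the protocol team created the list, section 11.3 says only that an investigator randomizes, and no section says that later rows are visible. Nor do investigators handle all contact with the women, since the midwife gives the first information. This reply stands: exposure of the list is a possibility that the plan leaves open, not a practice that it describes.

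The second reply concerns size. Nothing in the documents gives a basis for a shift of 0.5 to 1.0 points, and 1.0 is half the planned effect of 2. The primary outcome is a within-woman change (T3 minus T1), so stable differences in pain level partly cancel. A recruiter would have to foresee the change over one session, some weeks before labor. This also stands. The 11% to 29% range shows sensitivity and is not an estimate, and the smaller 0.2-point shift barely moves the error rate.

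The safeguards listed above deserve credit as well. Even so, none of them keeps the list out of a recruiter's sight. Nor is this only missing detail, because staff could follow the written procedure exactly and still leave the next allocation open to those who enrol.

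**Conclusion.** The point holds as a gap in the design. The section meant to describe concealment describes none, the investigators who recruit also assign from an Excel list, and the plan contains nothing that hides the next allocation from them. It does not follow that the list was open, that all 38 allocations were predictable in practice, or that bias occurred.

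The size of any bias is unknown. If selection shifted the expected outcome by 0.5 to 1.0 points, the false-positive rate would be about 11% to 29% instead of 5%. That rests on an assumed shift, SD 2 and 17 evaluable women per arm. The change should be made because it is cheap and the weakness cannot be repaired afterwards. If concealment already exists in practice, the protocol should say so.

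**What to change.** Rewrite sections 11.2 and 11.3 to state four things:

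1. The sequence is generated and held by a named role with no part in recruitment. The study nurse mentioned in section 11.3 could serve only if it is confirmed that the nurse does not recruit; otherwise another existing staff member should.
2. Recruiters have no access to the Excel file.
3. Allocations are released one at a time in sequentially numbered, opaque, sealed envelopes.
4. An envelope is opened only after eligibility and signed consent are recorded and the study number is written on it.

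The cost is 38 envelopes, minor preparation work and a few sentences of protocol text. No clinical care changes. One limit remains: because investigators are unblinded and know past assignments, they could still guess better than chance, about 70% correct under the block sizes assumed above.

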11.4 ANALYSIS

First descriptive analysis will be performed. Qualitative data will be described by frequency and percentage. Quantitative data will be described by mean, standard deviation, median, minimum, and maximum numbers.

Regarding the primary outcome, NRS pain score before and after the intervention will be compared using paired t-test or Mann-Whitney test, depending of data distribution. 95% confidence intervals will be provided.

Regarding secondary outcomes, chi-squared tests will be used to compare frequencies and rates between groups. In case of small cell sizes, we will alternatively use the Fisher's exact test. T-Test or Mann-Whitney test will be used to determine if there is a significant difference between means of the two groups. T-Test or Mann-Whitney test will be also used for all continuous data normally distributed or not such as NRS, Likert scale and physiologic data. Repeated measurements such as Anxiety and Nausea will be handled with appropriate techniques such as paired tests.

Safety variables include the incidence of Serious Adverse Events (SAEs), discomfort and the quality of immediate and distant labor pain analgesia. These data will be tabulated by treatment groups and overall, in contingency table for percentages or in descriptive univariate analyzes for continuous variables.

The Intent-to-Treat (ITT) population will be used for all efficacy and safety analyzes unless otherwise specified. This ITT analysis will include all randomized patients, according to their allocation group.

The Per-Protocol (PP) population will be used to validate the effectiveness of the studied intervention, as specified by the primary outcome. This PP analysis will include all patients in the ITT population who do not have a major violation of the protocol. The list of major violations includes at least:

- Non-administered medication
- Failure to meet an inclusion or exclusion criterion

Patients identified as having major violations will be screened to determine their final exclusion from the PP population, prior to the freezing of the database.

12.QUALITY CONTROL AND QUALITY ASSURANCE

Increased adherence to the protocol is acquired by multiple information sessions about the study for the midwives. Furthermore, a reminder poster will be displayed in their office. Adherence to the protocol by the participants will be monitored daily by a non-blinded investigator (LP) by looking at the daily reports of the study.

Patients will be well informed in advance about the study and the intervention on the prenatal visit. The informed consent must be signed to be included.

We refer to the section data handling to remind that we have attention for the privacy of the patient and their data. They will remain anonym participants.

Furthermore, we use standard forms with standard questions who are the same for every patient. (Questionnaire 1-4) Suggestive questions and subjective evaluations are not accepted. Also, the standard of care is a standardized protocol for every woman in active labor.

Important protocol modifications will be communicated to relevant parties. See appendix 'Clinical study agreement' Article 3 'Clinical study – Changes or modifications'.

13.ETHICAL ASPECTS

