4.1.2. Alternatives to standard of care

Audio-analgesia, aromatherapy, biofeedback, acupressure, TENS (Transcutaneous Electric Neurologic Stimulation) and massage are popular methods but are not proven to have a significant effect on labor pain. These are not available in our institution. On the other hand hydrotherapy, acupuncture and hypnosis have a proven significance as a tool for pain management during labor.^{xiii} More specifically hypnosis may reduce the overall use of analgesia during labor.^{xiv}

4.1.3. *Hypothesis*

Our primary goal is to evaluate the analgesic benefits of Virtual Reality Hypnosis (VRH) compared to the standard of care (ST) solely.

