5. STUDY OBJECTIVES

5.1 PRIMARY OUTCOME

The primary endpoint is to compare the differences in NRS pain measured before and after the intervention during labor. (T3 minus T1) The Pain Numerical rating Scale (NRS) is a scale from 0 to 10 well known by the medical staff.^{xv xvi}

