5.2 SECONDARY OUTCOMES

30 min after the end of the intervention the NRS pain is assessed once more. (T4)

During the intervention the comfort of the patient is evaluated. (T2) To do this we use the CPOT (Critical care Pain Observation Tool). CPOT is a comfort scale for (non)-ventilated patients in the intensive care unit. We decided to use this score, because during the VR experience we cannot communicate with the patient, which is similar as in sedated patients. And in our own experience we see that the parameters that we look at to evaluate the comfort of the patient during a VR sedation are very similar to this scale. (Facial expression, body movements, muscle tension and vocalization together make a score of 0 to 8)^{xvii} Vital signs like heart rate and blood pressure are parameters that are easily measured during the intervention and considered as objective for evaluating pain during labor. (T1,2,3,4) ^{xviii}

Nausea is also actively evaluated. Therefore we use the PONV rating scale from 0 to 3. (T1, T3, T4) Anxiety is evaluated with the NRS at the same time. (T1, T2, T3) We use the Likert satisfaction scale (from 0 to 5) to explore the satisfaction directly after their experience and the day after delivery. (T3, T6)

Willingness to repeat the intervention and to recommend the intervention can correlate with satisfaction of the overall experience. (T6)

Progression of labor is followed with the degree of the cervix dilatation, therefore we will not perform more cervical examinations than needed but interpret the measurement of the midwives/obstetricians. (T5)

The midwives are asked to evaluate the therapeutic link between themselves and the patient (NRS) after the women return to the maternity ward. (T5)

All the medication received during the stay on the delivery ward, adverse events and interruptions from the intervention is noted. (T3, T5)

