6. STUDY DESIGN

The VRH4L trial is an interventional, randomized, controlled, single-center, parallel group trial. Randomization will be done as a block randomization with a 1:1 allocation^{xix}

Clinique Saint-Jean Brussels (SJ), where the study takes place, is an academic hospital in the center of Brussels with around 2000 deliveries per year.

We create two groups: the VRH group and the control group. During the intervention (T1-3) the VRH-group receives a digital sedation in contrary to the control group who will not use the VRH headset.

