9. SCHEDULE OF ASSESSMENTS AND PROCEDURES

RCT T	TO	T1	T2	T3	T4	T5	T6
Delivery Phase	Prenat consult	Active Labor (study threshold) Day 0	Labor	Labor	Labor	End of Delivery	Day 1
		Before the Start AQUA	During AQUA	End AQUA	T3+30 min		
Screening/ ICF	X						
Refusal questionnaire	X						
Patient Questionnaires & Observation							
NRS pain		X		X	X		
Nausea		X		X	X		
Likert satisfaction							X
CPOT (VR comfort scale)			X				
Willingness to repeat (intervention)							X
Recommend (intervention)							X
Practitioner questionnaire							
Monitored contractions (on the CTG during intervention)				X			
Satisfaction midwife						X	
Quality of the therapeutic relationship						X	
Objective criteria							
Vital signs (Saturation)		X	X	X	X		
Medication received							X
Epidural				X	X		
Progression of labor							X
(Serious) adverse events		X	X	X	X	X	
Stop of digital sedation session				X			

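### The primary outcome is assigned a before/after test with no contrast between arms, although the hypothesis, design and sample size all compare the two arms

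*Combined protocol and SAP*

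**What the plan says.** Section 11.4 gives the primary outcome one sentence on testing: "NRS pain score before and after the intervention will be compared using paired t-test or Mann-Whitney test, depending of data distribution". It promises 95% confidence intervals but does not say of what. No arm, group contrast or treatment-effect estimate appears.

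The rest of the plan is comparative:

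- Section 4.1.3 sets the goal as to "evaluate the analgesic benefits of Virtual Reality Hypnosis (VRH) compared to the standard of care (ST) solely".
- Section 6 states: "The VRH4L trial is an interventional, randomized, controlled, single-center, parallel group trial".
- Section 11.1 sizes the trial on a 2-point difference in mean NRS pain between arms, SD 2 in each, 80% power, two-sided 5%, giving 17 evaluable women per arm and 38 in total after 10% dropout.
- Section 5.1 defines the variable as T3 minus T1: "The primary endpoint is to compare the differences in NRS pain measured before and after the intervention during labor". It does not say between whom the differences are compared.

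Between-group tests do appear in 11.4, in the next paragraph, which opens "Regarding secondary outcomes, chi-squared tests will be used to compare frequencies and rates between groups". There a t-test or Mann-Whitney test is set for means of the two groups, and then: "T-Test or Mann-Whitney test will be also used for all continuous data normally distributed or not such as NRS, Likert scale and physiologic data".

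**The concern.** Taken literally, a paired before/after test credits VRH with any change from T1 to T3 that both arms share, for example from standard care given on request (4.1.1) or from a shift in labour pain itself. It does not use the control arm, which is the reason for randomising.

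The two named tests are also not a parametric and non-parametric version of one analysis. A paired t-test is within-patient; Mann-Whitney is for two independent samples. Letting the data distribution decide between them can change the hypothesis tested, not just the method.

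At stake are the 5% error rate for the VRH effect and a reader's ability to know beforehand which result is primary.

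**Working it through.** **1. Which test was the trial sized for?** Inputs from 11.1: difference 2, SD 2, two-sided 5%, 80% power.

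Two-sample t-test, n per arm: noncentrality = 2 / (2 × √(2/n)). At n = 17 this is 2.92 on 32 df.

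| n per arm | Power |
|---|---|
| 16 | 78.1% |
| 17 | 80.7% |

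The plan's 17 is reproduced, and 17 / 0.9 = 18.9, rounded up to 19 per arm. A paired test of a 2-point change would need 14, 10 or 7 pairs at a T1–T3 correlation ρ of 0.3, 0.5 or 0.7. The sample size therefore belongs to a between-arm test.

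**2. What does the paired test do when VRH has no effect?** Assumptions not in the documents: SD 2 at both T1 and T3, ρ from 0.3 to 0.7, a fall in pain common to both arms, and the test applied to the 17 women in the VRH arm.

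SD of change = 2 × √(2(1 − ρ)) = 2.37, 2.00, 1.55. Noncentrality = fall / (SD of change / √17), on 16 df. For a 1-point fall at ρ = 0.5 this is 1 / (2/√17) = 2.06.

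| Shared fall | ρ = 0.3 | ρ = 0.5 | ρ = 0.7 |
|---|---|---|---|
| 0.5 point | 13% | 16% | 24% |
| 1 point | 37% | 49% | 71% |

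These are the chances of a significant result with no VRH effect. Pooling both arms (34 women) gives 22%, 29% and 45% for a 0.5-point fall, and 67%, 81% and 96% for 1 point.

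**3. Does the entry rule change this?** Sections 3 and 10 require NRS ≥ 4 before VRH is offered, which invites regression to the mean. Simulation: 40,000 trials per cell, integer NRS 0 to 10, T1 ≥ 4 assumed in both arms, underlying mean 5 to 7, ρ 0.3 to 0.7.

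| No VRH effect | Paired test, VRH arm | ANCOVA between arms |
|---|---|---|
| No shift, mean 5 | 10–16% | about 5% |
| No shift, mean 6 | 6–8% | about 5% |
| No shift, mean 7 | about 5% | about 5% |
| Fall of 0.5, means 5–7 | 18–47% | about 5% |
| Fall of 1, means 5–7 | 46–88% | about 5% |

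The entry rule alone adds little unless the mean is near 5. The shared fall does the damage.

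**4. What if pain rises in both arms?** Same simulation, true VRH benefit of 2 points.

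| Shared rise | Paired test, VRH arm | ANCOVA between arms |
|---|---|---|
| 1 point | 47–88% | 81–97% |
| 0.5 point | 77–99% | 81–96% |

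With a 1-point rise and mean 5 the loss is small (79–88% against 82–97%).

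**5. What power do valid contrasts have at 17 per arm?** Effect 2, no entry rule.

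| Between-arm contrast | ρ = 0.3 | ρ = 0.5 | ρ = 0.7 |
|---|---|---|---|
| T3 minus T1, two-sample t-test | 67% | 81% | 95% |
| T3 alone, two-sample t-test | 81% | 81% | 81% |
| ANCOVA of T3 adjusted for T1 | 83% | 89% | 97% |

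**The case against.** The strongest reply is that the plan omits the contrast rather than rejecting it. Section 5.1 speaks of comparing differences, Mann-Whitney is a two-sample test, the ITT analysis follows allocation, and 11.4 provides between-group tests for all continuous data, naming NRS. On that reading the authors meant a between-arm test of paired differences and wrote it loosely.

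As to intent, this is probably right. As to what is specified, it does not succeed. The between-group sentences stand under secondary outcomes, where NRS has its own referents: "30 min after the end of the intervention the NRS pain is assessed once more" is a secondary outcome in 5.2, and so are anxiety and the therapeutic relationship. The same paragraph assigns paired tests to repeated measurements, so the authors use the term in its ordinary within-patient sense. The ITT sentence fixes a population, not a test.

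A second objection is that the error rates depend on one reading (the paired test in the VRH arm) and on assumed values of ρ, mean and shift. That is fair. The documents give no direction for the shift, and with none the error rate is close to 5% at means 6 and 7. But the pooled reading gives higher error rates under a shared fall, and the logical defect does not depend on these values.

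Third, preferring ANCOVA to another between-arm contrast is a judgement. That also stands: other contrasts would be valid.

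**Conclusion.** The concern holds and must be fixed before the data are analysed. As written, the primary test does not address the VRH-versus-control question, and the distribution-dependent choice leaves the primary result open.

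The main consequence is loss of validity. If both arms improve by 0.5 to 1 point, the false-positive rate of the VRH-arm paired test is 13% to 71% without the entry rule and 18% to 88% with it, instead of 5%. Loss of power when pain rises in both arms is a lesser problem and is negligible in some settings.

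The sizes rest on 17 per arm, SD 2 at each time (11.1 gives it for NRS pain without a time-specific value), ρ 0.3 to 0.7, underlying mean 5 to 7, and the stated shifts. The sample size itself is not in error; it fits a between-arm test that the analysis section does not specify.

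**What to change.** Replace the sentence in 11.4 with one pre-specified between-arm analysis, for example:

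> The primary analysis is an ANCOVA of NRS pain at T3 on randomised arm, adjusted for NRS pain at T1, in the ITT population, reported as the adjusted mean difference (VRH minus control) with 95% CI and a two-sided 5% test. A Mann-Whitney test of T3 minus T1 between arms is a sensitivity analysis. Within-arm before/after comparisons are descriptive.

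Remove the switch that depends on data distribution. If the sponsor prefers the change score of 5.1, a two-sample t-test of T3 minus T1 is valid but needs 23 per arm for 80% power at ρ = 0.3 (17 at ρ = 0.5). A T3-only t-test matches 11.1. ANCOVA is preferred for power.

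Three short additions make the contrast computable; the main finding does not depend on them:

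- State when T1 and T3 are recorded in control patients. The section 9 schedule labels T1 only as "Before the Start AQUA" and T3 by the end of the same session, which controls do not have.
- State how a missing T3 is handled. Section 10 treats women who refuse or remove the headset as dropouts, while the ITT population in 11.4 keeps everyone randomised.
- State how the analysis treats an epidural recorded by T3.

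The test itself costs one paragraph of SAP wording, with no new assessments and no extra patients under ANCOVA or a T3-only test. The control-arm time points take one line, which may also need to be carried into the data collection form. Missing T3 and epidural take one or two lines.

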11. STATISTICAL CONSIDERATIONS AND ANALYTIC PLAN

11.1 SAMPLE SIZE

The sample size of the study is computed on the basis of expectations for the the difference of the pain NRS means between the two arms at final analysis. Based on previous studies (Yildrim 2004 and Harmon 1990), we may expect a difference of the pain NRS means of 2 or more between the two arms, with a standard deviation of the pain NRS of 2 in both arms. For a statistical power of 80%, an alpha error of 5% and a two-sided test, 17 evaluable patients are needed in each group to reach statistical significance (calculation performed with Stata/MP 14.1).

Assuming a potential drop out rate of 10% in each arm, a total of 19 patients need to be randomized to each arm. The total number of patients for the study is 38.

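### The primary-outcome sentence in 11.4 offers a paired t-test and a Mann-Whitney test as alternatives, but they do not test the same hypothesis, and read literally the Mann-Whitney branch ignores the pairing and loses power

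*Combined protocol and SAP*

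**What the plan says.** - Section 11.4, primary outcome: "NRS pain score before and after the intervention will be compared using paired t-test or Mann-Whitney test, depending of data distribution". The next sentence adds that "95% confidence intervals will be provided", with no interval method named.
- Section 5.1: the endpoint is to "compare the differences in NRS pain measured before and after the intervention during labor. (T3 minus T1"). Section 9 schedules NRS pain at both T1 and T3, so each woman contributes a pair.
- Section 4.1.3 puts the question between arms: "Our primary goal is to evaluate the analgesic benefits of Virtual Reality Hypnosis (VRH) compared to the standard of care (ST) solely".
- Section 11.1 also sizes the trial between arms, on a difference of 2 with SD 2: "For a statistical power of 80%, an alpha error of 5% and a two-sided test, 17 evaluable patients are needed in each group".
- Elsewhere in 11.4, Mann-Whitney is the rank test for comparing the two groups, and repeated measures such as anxiety and nausea are assigned paired tests. No section names a signed-rank test.

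**The concern.** The rule picks between two tests according to the shape of the data, so both should answer the same question. They do not. The paired t-test works on each woman's own change. Mann-Whitney assumes two independent samples, and its null variance has no term for the correlation between T1 and T3. The rank counterpart of the paired t-test is the Wilcoxon signed-rank test.

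The rank branch could plausibly be used. NRS is a bounded whole-number score, few women are evaluable per arm, and section 10 sets a floor on T1 for the intervention arm: "When the women selected in the VR group are in active labor (NRS pain ≥ 4". If Mann-Whitney were then run on T1 against T3, a real change in pain could be missed in a trial of 38 women. If it were instead run on change scores between arms, the shape of the data would decide whether the primary hypothesis is within-woman or between-arm.

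**Working it through.** **1. The plan's own figure.** Inputs from 11.1: difference 2, SD 2, two-sided 5%, power 80%, dropout 10%.
- Normal approximation: n = 2 × (1.960 + 0.842)² × 2² / 2² = 15.7, so 16 per arm.
- Two-sample t-test (noncentral t): 16.71, so 17 per arm, with power 0.807 at 17.
- Dropout: 17 / 0.9 = 18.9, so 19 per arm and 38 in total.

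The stated figures reproduce, and they do so as a between-arm, two-sample calculation.

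**2. Why correlation matters.** For n women with common SD σ and T1-T3 correlation ρ, the mean change has variance 2σ²(1 − ρ)/n. An independent-sample test uses 2σ²/n. As a large-sample guide, its true two-sided level is therefore 2Φ(−1.96/√(1 − ρ)):
- ρ = 0: 5.0%
- ρ = 0.3: 1.96/0.837 = 2.34, giving 1.9%
- ρ = 0.5: 1.96/0.707 = 2.77, giving 0.6%

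**3. Simulation of the tests themselves.** From the plan: n = 17, SD 2, whole-number scores limited to 0-10. Assumed, because the plan gives neither: T1 mean 6.5, and ρ. There were 3,000 runs per setting. Mann-Whitney was run on T1 against T3, and signed-rank on T3 minus T1.

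| ρ | False positives, Mann-Whitney / signed-rank | Power at 1 point | Power at 2 points |
|---|---|---|---|
| 0 | 4.3% / 5.0% | 28% / 27% | 77% / 76% |
| 0.3 | 2.2% / 4.3% | 24% / 36% | 80% / 89% |
| 0.5 | 0.9% / 4.8% | 22% / 45% | 84% / 96% |
| 0.7 | 0.1% / 5.7% | 17% / 66% | 90% / 99.8% |

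Repeat simulations agree to within about a percentage point or two, with or without limiting scores to 0-10. Imposing the floor of 4 at T1 raises power for both tests but keeps the gap: at ρ = 0.5 and a 1-point change, 30-32% against 54-59%, depending on how the floor is applied.

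**4. Intervals.** If the 95% CI were the independent-sample Hodges-Lehmann interval, simulated coverage would be about 99.8% or more at ρ of 0.3 and above. Part of that excess comes from rounding, since coverage is already about 99% at ρ = 0.

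**5. The other reading.** Mann-Whitney on T3 minus T1 between two arms of 17 held its level, at 4.5% to 5.2% over ρ from 0 to 0.7. It is a valid test of the between-arm question.

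**The case against.** The strongest reply is that the authors meant Mann-Whitney on change scores between arms. Sections 4.1.3, 5.1 and 11.1 all fit that reading, and 11.4 uses Mann-Whitney as a two-group test elsewhere. This is a fair reading, and on it the rank branch is sound. It does not rescue the sentence, because the paired t-test then becomes the branch that tests something else.

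Other points on that side also stand:
- The loss depends on a correlation that the plan does not give, and it vanishes at zero.
- At a 2-point change Mann-Whitney still has 80% power or more at ρ of 0.3 and above. The plan's 2 is a between-arm difference, however, so no within-woman effect is documented.
- The branch may be used in a minority of cases. If a Shapiro-Wilk test on the differences were the trigger, which the plan does not say, it was taken in about 12-27% of simulated runs.

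Three stronger conclusions are tempting, and the documents do not support them:
- A reader might infer that the promised 95% CI is wrong. Section 11.4 names no interval method, so this holds only if the independent-sample rank interval is used.
- A reader might infer a risk of excess false positives. That needs a negative within-woman correlation (7.6% at −0.3 in the simulation), and nothing in the documents suggests one.
- A reader might extend the fault to nausea and anxiety, but 11.4 already assigns these to paired tests.

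**Conclusion.** The sentence is wrong as written on either reading: its two branches address different hypotheses. Taken literally, the harm is lost power and, if the matching interval is used, an over-wide CI. With 17 women, SD 2 and an assumed correlation of 0.3 to 0.5, the actual level falls to between about 2% and just under 1%, and power for a 1-point change falls from about 35-46% with signed-rank to about 22-25%. Zero correlation gives no loss, and a higher correlation gives more.

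Replacing Mann-Whitney with signed-rank would not by itself repair the primary analysis. Both branches would then be before/after comparisons, while the hypothesis and the sample size are between-arm. This should be corrected, in the same edit that states the between-arm comparison.

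**What to change.** Reword the primary-outcome sentence in 11.4:
- The primary analysis compares each woman's T3 minus T1 change between the VRH and control arms, in line with 4.1.3 and 11.1. Use a two-sample t-test or, if the changes are non-normal, Mann-Whitney on the change scores, each with its matching 95% CI.
- Any within-arm before/after comparison uses the paired t-test or the Wilcoxon signed-rank test with its Hodges-Lehmann estimate and 95% CI. Mann-Whitney is not applied to T1 against T3.

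The cost is a sentence or two, with no new data, patients or procedures. The 17 evaluable and 19 randomized per arm are unchanged. It would help to say in 11.1 that the SD of 2 is meant for the change score. With SD 2 at each time point, the SD of the change is 2 × √(2(1 − ρ)), which equals 2 only at ρ = 0.5.
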